## SECTION VI: POTENTIAL BENEFITS

**Potential Benefits:** Identify any benefits that may be reasonably expected to result from the research, either to the subject(s) or to society at large. (*Note: Payment of subjects is not considered a benefit in this context of the risk-benefit assessment.*)

There are no direct benefits to the nonsmoking subjects for participating in this study. Smoking subjects receive smoking cessation support to abstain from tobacco smoking. This research will benefit scientific knowledge by contributing to the understanding of the use of PET imaging in tobacco addiction and schizophrenia. This may have clinical application in the future.

## SECTION VII: RESEARCH ALTERNATIVES AND ECONOMIC CONSIDERATIONS

1. **Alternatives:** What alternatives are available to the study subjects outside of the research?

The alternative to participation in this research protocol is to not participate. Subjects will be informed that they are free to choose not to participate and, if they do agree to become a subject, they will be free to withdraw from the study at any time during its course. They will also be informed that if they choose not to participate or if they withdraw, it will not adversely affect their relationship with their doctors or the hospital (see attached Consent Form).

2. **Payments for Participation (Economic Considerations):** Describe any payments that will be made to subjects and the conditions for receiving this compensation.

The subjects will be compensated for their time commitment and inconveniences necessary for completing the study. Subjects will have no financial responsibilities for any portion of the study. For all Aims compensation may be \$550 for each NCFHEB PET scan, \$350 for each PHNO PET scan, \$50 for each arterial line placement and \$50 for each MRI scan and \$40 for cognitive testing at baseline. Subjects who participate in the Probabilistic Reward Task may also be compensated for the amount that they “win” during the task, up to \$60. Subjects may also receive an extra \$10 for each Cold Pressor Task that they participate in. Subjects who complete the Conditioned Hallucinations Task (Hearing Task in the Consent) will receive \$75. Subjects will be paid either by check, and are advised to allow 4-6 weeks for receipt of payment, or they will be given a credit card or cash. In addition, subjects will be provided with a light meal, at the end of the PET imaging day. Reasonable transportation costs will be reimbursed. Receipts must be submitted. If participation in the PET Scan has already begun, then compensation will be based on involvement in the study, and will be up to the discretion of the PI.

Smokers will also receive \$10 for each contingency management appointment at which their carbon monoxide and urine cotinine levels show that they have not smoked. Subjects can decide if they want to receive this amount at each appointment in cash, or receive it all at the end of the study in the form of a credit card or check or cash. Smokers will receive an additional \$100

bonus for completing the study. Aim 6 subjects will receive an additional \$100 on PET day because of the longer scan day they will encounter as a result of the bolus to infusion scan. Subjects with schizophrenia: Because smoking subjects with schizophrenia will be asked to participate in the smoking cessation part of the study as inpatient, a different payment schedule was devised (as in HIC 27532). Subjects will be paid \$25 for first day of smoking cessation, \$50 for second, \$75 for third, etc (increments of \$25 for each successful day, for up to \$525). Thus, smokers with schizophrenia may earn up to \$1325 for smoking cessation, PET and MRI scans. Nonsmokers with schizophrenia may earn up to \$800.

**Cancellations:** If a PET scan should get cancelled for a reason outside of the subject's control (i.e. radiotracer synthesis failure) the subject will be paid \$50 minimum, or a higher amount not to exceed the payment for a full scan day. The amount of the payment for cancellation will be based on the subject's length of participation on that scan day prior to the cancellation, and will be up to the discretion of the PI.

3. **Costs for Participation (Economic Considerations):** Clearly describe the subject's costs associated with participation in the research, and the interventions or procedures of the study that will be provided at no cost to subjects.

There will be no costs to subjects related to participation in this research intervention.

4. **In Case of Injury:** This section is required for any research involving more than minimal risk.
- a. Will medical treatment be available if research-related injury occurs?
  - b. Where and from whom may treatment be obtained?
  - c. Are there any limits to the treatment being provided?
  - d. Who will pay for this treatment?
  - e. How will the medical treatment be accessed by subjects?

Medical treatment will be offered to the subjects for any physical injuries that they receive as a result of participating in this research. However, the subject or his/her insurance company is responsible for the cost. Federal regulations require that subjects be told that if they are physically injured, no additional financial compensation is available.

**Investigator Interests:**

Does the principal investigator, or do any research personnel who are responsible for the design, conduct or reporting of this project or any of their family members (spouse or dependent child) have an incentive or interest, financial or otherwise, that may affect the protection of the human subjects involved in this project, the scientific objectivity of the research or its integrity? Note: The Principal Investigator (Project Director), upon consideration of the individual's role and degree of independence in carrying out the work, will determine who is responsible for the design, conduct, or reporting of the research.

See Disclosures and Management of Personal Interests in Human Research

<http://www.yale.edu/hrpp/policies/index.html#COI>

Yes       No

Do you or does anyone on the research team who is determined by you to be responsible for the design, conduct or reporting of this research have any patent (sole right to make, use or sell an

invention) or copyright (exclusive rights to an original work) interests related to this research protocol?

Yes             No

If yes to either question above, list names of the investigator or responsible person:

*The Yale University Principal Investigator, all Yale University co-investigators, and all Yale University individuals who are responsible for the design, conduct or reporting of research must have a current financial disclosure form on file with the University's Conflict of Interest Office. Yale New Haven Hospital personnel who are listed as con-investigators on a protocol with a Yale University Principal Investigator must also have a current financial disclosure form on file with the University's Conflict of Interest Office. If this has not been done, the individual(s) should follow this link to the COI Office Website to complete the form:*

<http://www.yale.edu/coi/>

NOTE: The requirement for maintaining a current disclosure form on file with the University's Conflict of Interest Office extends primarily to Yale University and Yale-New Haven Hospital personnel. **Whether or not they are required to maintain a disclosure form with the University's Conflict of Interest Office, all investigators and individuals deemed otherwise responsible by the PI who are listed on the protocol are required to disclose to the PI any interests that are specific to this protocol.**

**Billing Information:** IRB Review fees are charged for projects funded by Industry or Other For-Profit Sponsors. If this study is funded by Industry or Other For-Profit Sponsor, provide the Name and Address of the Sponsor Representative to whom the invoice should be sent. *Note: the PI's home department will be billed if this information is not provided.*

**SECTION I: GENERAL INFORMATION**

1. **Performing Organizations:** Identify the hospital, in-patient or outpatient facility, school or other agency that will serve as the location of the research. Choose all that apply:

**b. External Location[s]:**

- |  |  |
|--|--|
|  APT Foundation, Inc.                                  |  Haskins Laboratories                  |
|  Connecticut Mental Health Center                      |  John B. Pierce Laboratory, Inc.       |
|  Clinical Neuroscience Research Unit (CNRU) |  Veterans Affairs Hospital, West Haven |

Other Locations, Specify: International Research Site  
(Specify location(s)):

2. **Probable Duration of Project:** State the expected duration of the project, including all follow-up and data analysis activities.

5 years

3. **Research Type/Phase: (Check all that apply)**

a. **Study Type** Single Center Study Multi-Center StudyDoes the Yale PI serve as the PI of the multi-site study? Yes  No  Coordinating Center/Data Management Other:b. **Study Phase** N/A Pilot Phase I Phase II Phase III Phase IV

4. Is this study a clinical trial? Yes  No

*NOTE the current ICMJE (International Committee of Medical Journal Editors) definition of a clinical trial: "any research study that prospectively assigns human participants or groups of humans to one or more health-related interventions to evaluate the effects on health outcomes." Health-related interventions include any intervention used to modify a biomedical or health-related outcome (for example, drugs, surgical procedures, devices, behavioral treatments, dietary interventions, and process-of-care changes). Health outcomes include any biomedical or health-related measures obtained in patients or participants, including pharmacokinetic measures and adverse events"*

If yes, where is it registered?

Clinical Trials.gov registry 

Other (Specify)

Registration of clinical trials **at their initiation** is required by the FDA, NIH and by the ICMJE.

*If this study is registered on clinicaltrials.gov, there is new language in the consent form and compound authorization that should be used.*

For more information on registering clinical trials, including whether your trial must be registered, see the YCCI webpage, <http://ycci.yale.edu/researchers/ors/registerstudy.aspx> or contact YCCI at [contact])

5. Will this study have a billable service as defined by the [Billable Service Definition](#)?

Yes  No 

If you answered "yes", this study will need to be set up in Patient Protocol Manager (PPM)

<http://medicine.yale.edu/ymg/systems/ppm/index.aspx>

6. Are there any procedures involved in this protocol that will be performed at YNHH or one of its affiliated entities? Yes \_\_\_ No X *If Yes, please answer questions a through c and note*

*instructions below. If No, proceed to Section II.*

- a. Does your YNHH privilege delineation currently include the **specific procedure** that you will perform?
- b. Will you be using any new equipment or equipment that you have not used in the past for this procedure?
- c. Will a novel approach using existing equipment be applied?

If you answered “no” to question 6a, or "yes" to question 6b or c, please contact the YNHH Department of Physician Services ([name]) for prior approval before commencing with your research protocol.

## SECTION II: RESEARCH PLAN

1. **Statement of Purpose:** State the scientific aim(s) of the study, or the hypotheses to be tested. Tobacco smoking is one of the only leading causes of death that is 100% preventable. While most smokers express a desire to quit smoking, only ~6% achieve abstinence in a given year and the majority relapse in the first 2 weeks. This highlights the acute withdrawal period as the critical window in maintaining abstinence. Nicotine is the primary addictive chemical in tobacco smoke and exerts its initial reinforcing effects through the mesolimbic dopamine (DA) system(1). Specifically, nicotine binds to beta2 subunit-containing nicotinic acetylcholine receptors (beta2\*-nAChRs) located throughout the brain and this leads to widespread changes in neurotransmitter levels including dopamine (DA), and upregulation, i.e., increase in number, of beta2\*-nAChRs. beta2\*-nAChRs are also responsible for controlling the dynamic range of DA release, with chronic nicotine administration or deletion of the beta2\*-nAChRs resulting in reduced DA release(2). This suggests that chronic smokers may have blunted DA release compared to nonsmokers and that changes in DA may be tied to other neurochemical alterations in the brains of smokers. However, the basic dopaminergic mechanisms involved in withdrawal and relapse in tobacco smokers remain unknown.

We have a radiotracer at the Yale PET center that will allow us to measure dopaminergic neurotransmission in the brains of smokers. The radiotracer is called [C]PHNO and it has advantages over other dopamine D2 receptor ligands because it is an agonist and measures the high affinity, functionally active D2 receptors and not the low affinity D2 receptors. This has been recently shown to produce an increased sensitivity over other PET ligands to measure changes in synaptic dopamine levels and thus provides a novel paradigm to investigate drug-induced dopamine release, such as amphetamine-induced dopamine release. We have preliminary data suggesting tobacco smokers at approximately 2 weeks of abstinence have blunted DA release compared to nonsmokers. The overall goal of the study is to measure amphetamine-induced DA release during early and prolonged withdrawal in smokers (vs. nonsmokers) and to examine relationships to relapse and other clinical correlates of tobacco smoking.

**Aim 1. To determine amphetamine-induced DA release in nonsmokers and in tobacco smokers during acute and prolonged withdrawal.** We will scan 50 Healthy Smokers and 50

Non Smoker healthy controls. Each tobacco smoking subject will participate in up to 4 [C]PHNO PET scans, one pair of scans during the first 2 weeks of smoking abstinence and, for those who remain abstinent, the option to have another pair of scans at 2-8 weeks abstinence. We aim to have at least one week in between sets of scans. Ideally, two PET scans will be carried out in the same day. We first obtain a baseline scan, then approximately three hours before the second scan, amphetamine (0.5 mg/kg, PO) will be administered. Nonsmokers will only be asked to participate in one set of scans. We hypothesize that smokers at 1-2 weeks of withdrawal will have amphetamine-induced DA release that is blunted compared to healthy nonsmokers. We also hypothesize that the smokers who are scanned again at 2-8 weeks withdrawal will exhibit some ‘normalization’ of the dopamine system and will have a larger amphetamine-induced DA release compared to their first scan. We hypothesize that smokers with amphetamine-induced DA release similar to nonsmokers, or that increases over time, will have better abstinence outcomes.

2. **Background:** Describe the background information that led to the plan for this project. Provide references to support the expectation of obtaining useful scientific data.

**Tobacco Smoking:** There are enormous costs to society and to individuals from tobacco smoking addiction and related disease, e.g., ~80% of smokers will die from a smoking related disease. Smokers are clearly aware of the negative consequences; but 20% of the adult American population continues to smoke. Most smokers want to quit smoking and make yearly quit attempts, but only 6% are successful in a given year and the vast majority cannot quit for more than 2 weeks, *even with all of the currently available treatments*. We do not know how to help smokers remain abstinent. The behavioral manifestations of withdrawal symptoms are clear – cognitive dysfunction, intense craving, irritability, anxiety, and bad mood – but because tobacco smoking is also a brain-based addiction, it is imperative that we uncover the molecular mechanisms that drive these symptoms during acute and prolonged withdrawal. Understanding the time course of the molecular changes that occur over withdrawal and determining relationships between neurochemistry, clinical symptoms, and their predictive relationship to relapse will achieve several goals: 1) provide to the public a greater understanding of the neurobiological basis of tobacco smoking withdrawal, e.g., it is not just a “bad habit”; 2) provide the public and clinicians neurochemical data on how long the brain needs to recover from the addiction; 3) inform the field about directions we should take in terms of targeting new drug development and in creating more easily obtained biomarkers or “proxies” of dysfunctional neurotransmission over the first few months of withdrawal, to personalize treatment selection consistent with a smoker’s individual neurochemistry.

**How does the dopaminergic system regulate tobacco smoking and withdrawal?** A substantial literature demonstrates that nAChRs and the cholinergic system dynamically control the mesolimbic DA system by enhancing, inhibiting and filtering striatal DA release(3, 4). Nicotine releases DA by binding to  $\beta_2^*$ -nAChRs located on the mesolimbic DA neurons in the ventral tegmental area, resulting in neuronal firing and DA release in the nucleus accumbens and dorsal caudate (5).  $\beta_2^*$ -nAChRs are also critical for the reinforcing(6) and motivational effects of nicotine, e.g., tying cues to drug consumption(7). Nicotine also “filters” DA release by modifying the sensitivity of DA synapses through its desensitization of the nAChRs. As reviewed in Exley and Cragg (2008)(3), nicotine promotes DA release through both burst and tonic activity. Nicotine functions as an agonist and also as an antagonist via its desensitization/blocking actions and both may ultimately enhance DA neurotransmission. Thus,  $\beta_2^*$ -nAChRs are responsible for controlling the dynamic range of DA release. A recent

preclinical study reported that chronic nicotine administration or deletion of the  $\beta_2^*$ -nAChRs (i.e.,  $\beta_2^*$  knockout) reduced acute DA release(2). This suggests that chronic smokers may have a blunted stimulus-induced DA release compared to nonsmokers; however, this has not been examined. Several PET studies have demonstrated blunted amphetamine-induced DA release in the ventral striatum in both cocaine and alcohol dependent populations at approximately 2 weeks of withdrawal vs. controls(8-10). In the cocaine-dependent subjects, those with a more blunted drug-induced DA release responded less well to a behavioral treatment that incorporated positive reinforcement(10). Their findings suggest that individuals with dysfunctional DA transmission are not able to “switch” well from drug-reinforced behavior to more natural alternative rewards(8, 10), and this is supported by a preclinical study in which rats with a lesioned nucleus accumbens displayed an inability to choose greater magnitude delayed rewards vs. immediate rewards of lesser value(11). We have preliminary data suggesting tobacco smokers at approximately 2 weeks of abstinence have blunted DA release compared to nonsmokers.

**Imaging amphetamine-induced DA release in smokers vs. nonsmokers measured with [C]PHNO and PET.** Amphetamine administration results in a reliable and robust increase in extracellular DA and has been widely used in brain imaging studies as a marker of DA function in psychiatric and healthy populations(8, 9, 12-16). We have chosen oral amphetamine based on its robust and reliable DA signal and because it is routinely used in PET studies(17-23) and by our group to probe DA neurotransmission. The amphetamine robustly increases synaptic levels of DA. The increased DA competes with the radiotracer to bind at the DA receptor, thus an increase in DA results in a decrease in radiotracer binding compared to baseline. This allows calculation of the “occupancy” of the receptors by DA or a change in binding potential (BP), and is an indirect measure of DA release based on the “occupancy model”(13). We have obtained preliminary data that demonstrates blunted DA release in smokers at 2-3 weeks of abstinence vs. controls and is similar to what has previously been found in cocaine- and alcohol- dependent individuals(8, 9). While the previous studies(8, 9) used [C]raclopride which measures striatal D2/3 receptor binding, we propose to use [C]PHNO which measures striatal and extrastriatal (substantia nigra and globus pallidum) D2/3 binding(24). Importantly, blunted DA release in cocaine-dependent individuals was associated with the choice to self-administer cocaine over money(8) and with treatment failure(10). In the current study, we will determine whether smokers have blunted DA release compared to nonsmokers and if the degree of DA release in smokers is associated with time to relapse.

**3. Research Plan:** Summarize the study design and research procedures using non-technical language that can be readily understood by someone outside the discipline. Be sure to distinguish between standard of care vs. research procedures when applicable, and include any flowcharts of visits specifying their individual times and lengths.

**3.1 Overall plan for Aim 1: To determine amphetamine-induced DA release in nonsmokers and tobacco smokers during acute and prolonged nicotine withdrawal.** We will image up to 50 smokers and 40 nonsmokers.

**Smoker-subjects:** Subjects that qualify for the study will be asked to participate in the following:

- a) One MRI scan, which will take approximately 30-60 minutes. This will take place at the Anlyan Center at [name].
- b) Up to 8 weeks of smoking abstinence- meet with staff multiple times a week to ensure abstinence. For the first week the subject will meet with staff every day (barring an unforeseen circumstance that prevents the subject from meeting). Meetings will occur either at [name], the Yale PET center, or a meeting point midway between the subject and Yale due to distance. As the weeks proceed, meetings will taper down.
- c) Two sets of two PET scans with [C]PHNO approximately 1-2 weeks after quitting smoking and again at 2-8 weeks with at least a week break in between scan sets. Both scans of each set will take about 2 hours each and should be done on the same day. Starting up to 3 hours prior to the second [C]PHNO scan of the set, subjects will be asked to take a drug called amphetamine by mouth. These will take place at the Yale PET Center.

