## **PET**

PET scans may be performed on the High Resolution Research Tomograph (HRRT, 2-3 mm resolution) or another similar camera. Venous catheters will be used for i.v. administration of the radiotracers, venous blood sampling of activity, and for venous blood sampling of amphetamine plasma levels and hormone levels. At the beginning of scan, the subject's head will be immobilized and a transmission scan will be obtained for attenuation correction. PET scans will be acquired using bolus or bolus to infusion administration of up to 10 mCi of [C]PHNO and subjects will be scanned for up to 2 hours. Dynamic images of radioactivity concentration are reconstructed with corrections for attenuation, normalization, random events, scatter, and deadtime. Subject motion is corrected automatically on an event-by-event basis with the Vicra motion tracking system. Vital signs (blood pressure, pulse and respiration) are collected prior to and during each PET scan. Urine pregnancy test will be again administered on the PET scan day prior to the initiation of any imaging procedures. Smoking abstinence, when appropriate, will also be confirmed for smoking subjects prior to PET scanning.

PET scanning will then proceed as following for each aim:

Aim 1. Smoking subjects will be asked to come in for two [C]PHNO scans with amphetamine administration. The first scan will be during the first 2 weeks of withdrawal with the option to come back again at 2-8 weeks of withdrawal. Nonsmoking subjects will be asked to come in for one set of two [C]PHNO scans with amphetamine administration. Up to 10 mCi of PHNO will be administered per scan. After the first scan, subjects will take amphetamine (0.5mg/kg) by mouth, and then will be imaged again with PHNO. If technical difficulties arise, the second PET scan of the set may have to be re-scheduled and will be scheduled as soon as possible. In that case, subjects may be asked to re-take amphetamine on the day of the rescheduled PHNO scan, approximately 3 hrs prior to the scan. Amphetamine dose will not exceed 50mg per scan. Subjects will not be allowed to drive home.

In the rare event that a scan would fail post injection, subjects may repeat each scan set up to a total of 8 PHNO scans for smokers and 4 PHNO scans for nonsmokers.

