Regional [ $^{11}\text{C}$ ]PHNO uptake for each subject will be quantified as  $\text{BP}_{\text{ND}}$  described above for each ROI and will represent the primary outcome measure for the proposed experiments. Repeated measures ANOVA will be used to evaluate the change between scans ( $\Delta\text{BP}$ ) for brain measures for the scans.  $\Delta\text{BP}$  will be computed as  $[(\text{BP}_{\text{baseline}} - \text{BP}_{\text{condition}}) / \text{BP}_{\text{baseline}} \times 100]$ . Analysis will be conducted using SAS version 9.1 (Cary, NC).  $N=20$  subjects per group is necessary to detect differences between smokers and nonsmokers. Potential associations, e.g., relationship between magnitude of dopamine release and time to relapse, will be examined using correlation analysis with Type I error corrected for multiple comparisons. Exploratory analyses of the other cognitive and behavioral measures and their relationship to relapse will also be performed.

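### The relapse hypothesis counts rising DA release as favourable, but a rise can be seen only in smokers still abstinent at the second scan set, and the planned correlation does not exclude that bias

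*Combined protocol and SAP*

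**What the plan says.** All references are to the PHNO protocol in the combined document unless stated.

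- **Hypothesis** (Section II, item 1, Aim 1): "We hypothesize that smokers with amphetamine-induced DA release similar to nonsmokers, or that increases over time, will have better abstinence outcomes". This joins two predictors: a level, which the first scan set can show, and a change, which needs both sets.
- **Access to the second set** (same paragraph): "for those who remain abstinent, the option to have another pair of scans at 2-8 weeks abstinence". The PET section repeats that it is voluntary: "with the option to come back again at 2-8 weeks of withdrawal".
- **Timing** (section 3.1): the second set takes place "again at 2-8 weeks with at least a week break in between scan sets", so its day differs between smokers.
- **Outcome** (Section II, item 2, Background): the study will determine "if the degree of DA release in smokers is associated with time to relapse".
- **Analysis** (section 3.7, repeated under item 11, Statistical Considerations): "relationship between magnitude of dopamine release and time to relapse, will be examined using correlation analysis with Type I error corrected for multiple comparisons".

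Neither statistical section says when time to relapse starts, which scan set supplies the release value, whether change is limited to smokers scanned twice, or how a smoker without a second set is classed. No landmark or time-dependent method is planned.

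**The concern.** A smoker who relapses between the two sets can never be recorded as showing a rise. Unless that smoker's first scan already resembled a nonsmoker's, a literal test of the hypothesis puts them in the unfavourable group. Staying relapse-free until the second set is then a condition of entering one arm of the favourable group, and that abstinence is also counted as outcome.

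A survival model would not cure this. With the same grouping and time counted from quit day or the first scan, it would carry the same bias.

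At stake is a conclusion that dopamine recovery predicts abstinence, reached when the two are unrelated. The relation of DA release to relapse is part of the overall goal in the Statement of Purpose. The same aim also predicts that release will rise between sets. If it does, more rescanned smokers count as increasers and the artefact grows.

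**Working it through.** The plan gives no power or error rate for the relapse hypothesis, so there is no figure to reproduce. The check is what each analysis would do if DA release and relapse were unrelated.

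**Inputs from the documents.** 50 smokers (section 3.1); two-sided 0.05 (section 3.7); ventral striatal release of 21% (SD 12) in smokers and 29% in nonsmokers (pilot data, section 3.7, as size of reduction); second set at 2-8 weeks and at least one week after the first.

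**Assumptions.** Exponential relapse after the first set; follow-up of 180 days in the first simulation below. The PHNO protocol states no retention, so a range is used. The closed Aim 3 of the companion NCFHEB protocol expects about 50% abstinent at 4-8 weeks.

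**1. By hand.** First set on day 7, second on day 42, 50% of smokers still abstinent then, and half of those rescanned showing a rise by chance.

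- Rescanned: 50 × 0.5 = 25. Increasers: 25 × 0.5 = 12.5. Everyone else: 50 − 12.5 = 37.5.
- Relapsed before day 42: 0 of 12.5 increasers, and 25 of the 37.5 others (67%).
- Relapse rate: ln 2 / (42 − 7) = 0.0198 per day.
- Median time to relapse, increasers: 42 + 35 = 77 days.
- Median, others: 50 × (1 − exp(−0.0198 × (t − 7))) = 18.75 gives t ≈ 31 days.

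The gap of 77 against 31 days comes entirely from the grouping.

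**2. Simulation of the rise alone** (1,500 trials per row, Mann-Whitney test, no true link). Analysis (a) compares increasers with all other smokers from quit day. Analysis (b) compares them with non-increasers among smokers scanned twice, from quit day. Analysis (c) is (b) with time counted from the second scan.

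| Abstinent at day 42 | Second set | (a) | (b) | (c) | Mean scanned twice |
|---|---|---|---|---|---|
| 30% | day 42 | 99.4% | 4.2% | 4.2% | 14.9 |
| 50% | day 42 | 98.8% | 5.1% | 5.1% | 25.0 |
| 70% | day 42 | 79.2% | 4.2% | 4.2% | 35.0 |
| 30% | days 14-56 | 94.9% | 4.1% | 4.8% | 20.7 |
| 50% | days 14-56 | 88.4% | 4.6% | 4.3% | 29.5 |
| 70% | days 14-56 | 62.7% | 5.7% | 5.3% | 37.8 |

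Now let release normalise by an assumed 0.5 SD per two weeks, with the scan day spread over days 14-56. Analysis (b) then rises to 6.2%-9.0%. A rank correlation of change with time from quit day in smokers scanned twice gives 7.3%-11.8%. Both drift up because a later scan brings a larger change and also requires longer abstinence. Analysis (c) stays at 4.6%-5.1%.

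**3. Simulation of the full composite.** First set on day 10, second on days 17-56, similarity to nonsmokers taken as release of at least 29%, test-retest correlation 0.5-0.7, 28-day abstinence after the first set 0.40-0.75, and either no normalisation or an 8-point rise unrelated to relapse.

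- Composite grouping: rejects in roughly 45%-90% of trials. At 28-day abstinence of 0.5 with no normalisation, relapse by day 56 is about 55% against 80%, and median time to relapse about 52 against 28 days.
- Composite with only 70% of eligible smokers accepting the rescan: 22%-55%.
- Rank correlation of first-set release with time to relapse, all smokers: 4.5%-5.9%.
- Rank correlation of change with time from quit day, smokers with both sets: 4.4%-6.9%; about 11% with a 16-point rise.
- Change in smokers with both sets, time from the second scan: about 4%-5%.

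**The case against.** The strongest reply is that the composite is a sentence of hypothesis and not an analysis rule. Section 3.7 plans a correlation. It defines no favourable group, no cut-off and no group test; the dichotomy and the 29% threshold were supplied for this check. A correlation needs a number for each smoker, so one without a second set would have no change score and would drop out, not become a non-increaser. The preceding sentence of Aim 1 also confines normalisation to smokers who are scanned again, so the later wording can be read as continuing that restriction. Under that reading the false-positive rate is close to nominal.

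Most of this stands. A reader might infer that the planned analysis is biased by construction, or that the study will report a false link. The documents do not support that: the bias needs a grouping the analysis section does not specify. Nor do they support reading the background remark "only ~6% achieve abstinence in a given year and the majority relapse in the first 2 weeks" as a retention assumption. It describes smokers in general, whereas these smokers receive contingency management (section 3.8).

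What does not stand is the inference that nothing needs changing. The hypothesis as worded invites the biased comparison. The correlation text refers only to "relationship between magnitude of dopamine release and time to relapse", without saying which scan set, which smokers or which time origin.

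**Conclusion.** The concern holds in conditional form. Testing the composite as worded, with smokers lacking a second set in the comparison group, would carry guaranteed-abstinence bias. The illustrative false-positive rate is roughly 45%-90% when all eligible smokers are rescanned, and lower but still well above 5% when uptake is partial. The direction follows from the design. The size depends on assumed retention, relapse distribution, cut-off, test-retest correlation and uptake.

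The correlation in section 3.7 is nearly free of the problem if restricted to first-set release, or to change in smokers with both sets: about 5%-7%. With strong normalisation and a second scan day spread over 2-8 weeks, counting from quit day raises the latter to about 10%. The plan does not state those restrictions.

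A reader might also infer that the main result is at risk. It is not: the powered hypothesis is the smoker-nonsmoker comparison, which does not use relapse. The relapse association is secondary and has no power statement. Severity is moderate: it should be fixed, and the fix is a cheap improvement.

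**What to change.** Replace the composite in Aim 1 with two analyses, and carry them into section 3.7 and item 11:

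1. First-set DA release, as a continuous variable, against time to relapse counted from the first scan day, in all smokers with a first set.
2. Change from first to second set against time to relapse counted from the second scan day, only in smokers with both sets.

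State that a smoker without a second set is never classed as a non-increaser.

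The cost is rewording; no scans or visits are added. The downside is that analysis 2 uses only smokers scanned twice: about 15 to 38 of 50 in the scenarios tabulated above, and about 17 with 50% retention at day 42 and 70% uptake. Those are the only smokers in whom change is observed, so no information on change is lost.
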